5.9. Analysis of Anti-Drug Antibody Variables

The summary of ADA variables will be presented by treatment groups (Praluent, placebo) on the ADA population. No formal inferential testing will be performed. Summaries will be descriptive in nature.

ADA variables will be summarized, taking into account all samples regardless of timing in relation to injections. ADA results will be summarized as follows:

- ADA results (negative or positive) by time point
- Neutralizing status (negative or positive) by time point for positive ADA

- ADA titers using descriptive statistics (median, minimum and maximum) for positive ADA by time point
- Number (%) of patients with pre-existing ADA and number (%) of patients with treatment-emergent ADA positive response
- Number (%) of patients with persistent/indeterminate/transient treatment-emergent ADA positive response
- Time to onset of treatment-emergent ADA positive response using descriptive statistics.
- Number (%) of patients with at least 1 neutralizing ADA.

Correlations between ADA parameters (e.g., titers, treatment-emergent ADA positive status, neutralizing status) and safety and/or efficacy endpoints will also be explored (e.g., scatter plot).

[REDACTED] [REDACTED]
[REDACTED].

6. DATA CONVENTIONS

The following analysis conventions will be used in the statistical analysis.

6.1. Definition of Baseline for Efficacy and Safety Variables

Unless otherwise specified, the baseline assessment is programmatically defined as the latest available measurement taken before first administration of study treatment. For patients randomized but not-treated, the baseline will be the last available measurement before randomization.

6.2. Data Handling Conventions for Primary and Secondary Endpoints

Data handling conventions, including addressing missing data, is addressed for the primary and secondary endpoints in Section 5.6.1, 5.6.2, and 5.6.3.

6.3. General Data Handling Conventions

In general, the following formulas will be used for computation of parameters:

Time from diagnosis

Time from diagnosis (years) = (Date of informed consent – Date of diagnosis*) / 365.25.

(*):In case the month of diagnosis would be missing, it will be put equal to JANUARY if the year of diagnosis equals the year of informed consent; it will be put equal to JUNE otherwise. In the case the day is missing, the day will be put equal to 1st if the month and year of diagnosis equals the month and year of informed consent; otherwise it will be put equal to the 15th of the month.

Date of last dose of study treatment

The date of the last injection is equal to the last date of administration reported on injection administration case report form page, or missing if the last administration date is unknown.

Renal function formulas

Estimated GFR will be derived using the Modification of the Diet in Renal Disease (MDRD) equation:

$186.3 \times (\text{creatinine in } \mu\text{mol/L} / 88.4)^{-1.154} \times (\text{age in years})^{-0.203} \times 0.742 \text{ if female, } \times 1.21 \text{ if race is "black or African American".}$

Lipids variables, laboratory safety variables, hs-CRP

For data below the lower limit of quantification (LLOQ) / limit of linearity, half of the lower limit value (i.e., LLOQ/2) will be used for quantitative analyses. For data above the upper limit of quantification (ULOQ) / limit of linearity, the upper limit value (i.e., ULOQ) will be used for quantitative analyses.

6.4. General Missing Data Conventions

For categorical variables, patients with missing data are not included in calculations of percentages unless otherwise specified. When relevant, the number of patients with missing data is presented.

Handling of baseline definition if “time” of first study treatment administration or time of assessment at week 0 visit is missing

If the time of the first study treatment administration or the time of assessment at week 0 visit is missing, then the baseline value is defined as the last available value obtained before or on the day of the first study treatment administration.

Handling of computation of treatment duration and compliance if study treatment first or end of treatment date is missing

If the last or first injection date is missing, the exposure duration and compliance will be left as missing.

Handling of safety and efficacy analysis periods and survival analysis if end of study treatment date is missing

If the last injection date is missing, then this date is imputed to the earliest between:

- the last day of the month and year, when applicable or else the 31st of December of the year,
- the date of the end of treatment visit (week 96 visit for completer, early end of treatment visit for patients who prematurely discontinued the study treatment),
- the date of the last contact

for the purpose of safety and efficacy analysis period start and/or end.

Handling of medication missing/partial dates

No imputation of medication start/end dates or times will be performed. If a medication date or time is missing or partially missing and it cannot be determined whether it was taken prior or concomitantly, it will be considered a prior, concomitant, and post-treatment medication.

Handling of adverse events with missing or partial date/time of onset, worsening, seriousness

Missing or partial AE dates and times will be imputed so that if the partial AE date/time information does not indicate that the AE started prior to treatment or after the TEAE period, the AE will be classified as treatment-emergent. These data imputations are for categorization purpose only and will not be used in listings. No imputation is planned for date/time of AE resolution.

Handling of adverse events when date and time of first study treatment administration is missing

When the date and time of the study treatment administration is missing, all AEs that occurred on or after the day of randomization will be considered as TEAEs.

When the time of the first study treatment administration is missing, all AEs that occurred on the day of the first study treatment administration will be considered as treatment-emergent AEs.

Handling of missing assessment of relationship of adverse events to investigational medicinal product

If the assessment of the relationship to study treatment is missing, then the relationship to study treatment has to be assumed as possibly related in the frequency tables, but no imputation should be done at the data level.

Handling of potentially clinically significant abnormalities

If a patient has a missing baseline value he will be grouped in the category “normal/missing at baseline.”

For PCSAs with 2 conditions, one based on a change from baseline value and the other on a threshold value or a normal range, with the first condition being missing, the PCSA will be based only on the second condition.

For a PCSA defined on a threshold and/or a normal range, this PCSA will be derived using this threshold if the normal range is missing; e.g., for eosinophils the PCSA is >0.5 GIGA/L or $>ULN$ if $ULN \geq 0.5$ GIGA/L. When ULN is missing, the value 0.5 should be used.

Measurements flagged as invalid by the laboratory will not be summarized or taken into account in the computation of PCSA values.

6.5. Visit Windows for Time Points

Visit windows will be programmatically imposed on those efficacy and safety measures repeatedly collected over the course of the study. These visit windows are derived from the number of days in study, specifically assigning day ranges to mimic the study assessment

schedule provided in the protocol. Data analyzed by time point (including efficacy, laboratory safety data, vital signs, physical examinations, and ADA) will be summarized using the analysis windows given in Appendix 10.2. These analysis windows will be applicable for all analyses, and they are defined to provide more homogeneous data for time point-specific analyses. If multiple valid values of a variable exist within an analysis window, the nearest from the targeted study day will be selected. If the difference is a tie, the value after the targeted study day will be used. If multiple valid values of a variable exist within a same day, then the first value of the day will be selected when time is available, else the scheduled visit will be selected.

6.6. Unscheduled Assessments

For efficacy, safety laboratory data, vital signs, physical examinations, and ADA, unscheduled visit measurements may be used to provide a measurement for a time point, a baseline, a last or a worst value, if appropriate according to their definitions. The measurements may also be used to determine abnormal values and PCSA.

6.7. Pooling of Centers for Statistical Analyses

The randomization scheme was not stratified by center because the primary efficacy variable is centrally assessed and expected not to be influenced by the center when other factors such as diet are already controlled. Therefore, the center will not be added as factor in the primary analysis model.

6.8. Statistical Technical Issues

Not Applicable.

7. TIMING OF STATISTICAL ANALYSES

There are no interim analyses planned. Therefore, no multiplicity adjustment for multiple analyses is needed (see Section 5.6.4).

The statistical analysis will be conducted at the end of the study and will consist of the final analysis of primary and secondary endpoints and final safety analysis.

8. SOFTWARE

All analyses will be generated using SAS Version 9.4 or higher.

10. APPENDIX

10.1. Summary of Statistical Analyses

Primary Neurocognitive Endpoint Analysis:

Endpoint	Analysis Populations	Statistical Method	Supportive Analysis	Subgroup Analysis	Other Analyses
Change from baseline to week 96 in SWM strategy z-score	Primary Safety Population	MMRM	Yes, including handling of missing data	Yes	1) Actual stratification factor 2) Multiple Imputations + ANCOVA 3) Pattern Mixture Model

10.2. Windows for Analysis Time Points

Below are the definitions for the visit windows programmatically imposed on measures repeatedly collected over the course of the study. These visit windows reflect the study schedule of assessments as described in the protocol. The visit windows are constructed using ranges applied to the number of days in study (study days) when the measure is collected. Day 1 is defined as the first date of double-blind study treatment administration, and is labeled as baseline for most variables. Since the protocol specifies that measurements be collected before study treatment is administered on a given day, it is appropriate that baseline include Day 1. For randomized but not treated patients, Day 1 is the day of randomization.

Table 2: Analysis Windows Definition – All Endpoints Except Lipids or Vital Signs

Time point	Targeted study day	Analysis window in study days
Week 24	169	85 to 252
Week 48	337	253 to 420
Week 72	505	421 to 588
Week 96	673	589 to 756

Study days are calculated from the day of first IMP injection, the day of first IMP injection being Day 1. For randomized but not treated patients, Day 1 is the day of randomization.

Table 3: Analysis Windows Definition – Lipids

Time point	Targeted study day	Analysis window in study days
Week 8	57	29 to 70
Week 12	85	71 to 126
Week 24	169	127 to 252
Week 48	337	253 to 420
Week 72	505	421 to 588
Week 96	673	589 to 756

Study days are calculated from the day of first IMP injection, the day of first IMP injection being Day 1. For randomized but not treated patients, Day 1 is the day of randomization.

Table 4: Analysis Windows Definition – Vital Signs

Time point	Targeted study day	Analysis window in study days
Week 8	57	29 to 70
Week 12	85	71 to 126
Week 24	169	127 to 210
Week 36	253	211 to 294
Week 48	337	295 to 378
Week 60	421	379 to 462
Week 72	505	463 to 546
Week 84	589	547 to 630
Week 96	673	631 to 714

Study days are calculated from the day of first IMP injection, the day of first IMP injection being Day 1. For randomized but not treated patients, Day 1 is the day of randomization.

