Research samples (serum and plasma)			X			X		X				X	
			X										

ADA = anti-drug antibody, CPK = creatine phosphokinase, EOS = end of study, F/U = follow-up, HbA1c = hemoglobin A1c, hs-CRP = high-sensitivity

C-reactive protein, S = serum, TSH = thyroid-stimulating hormone, U = urine, WOCBP = women of childbearing potential

- Visit 2 is optional.
- Injection training will be performed with the patient and/or caregiver at visit 2, at visit 3, or at visits 2 and 3 using placebo. Refer to Section 5.1 for additional information on injection training.
- The patient or caregiver will administer the first dose of double-blind study drug in the clinic on day 1. The patient will be monitored for 30 minutes after the first dose. Subsequent doses of study drug must be administered Q2W. Study drug will be administered at home between week 84 and week 94. The last dose of study drug will be administered at home at week 94. Patients will come into the clinic for the last study visit at week 96.
- Injection supplies and the dosing log will be provided to the patient.
- See Appendix 6 for diet.
- Menstrual cycle data will be collected for women of childbearing potential who are not on hormonal contraceptives.

7. On days when a clinic visit coincides with a dosing day (visits 3, and 8), blood samples (including ADA samples) will be collected after study assessments are performed and before the dose of study drug is administered. At visits 4, 5, 6, 7, 9, 10, and 11, study drug may be administered prior to study assessments.
8. If a neurocognitive AE is reported during the visits when the test is not planned or in case of early treatment discontinuation, an unscheduled neurocognitive battery test will be performed.
9. Samples will be tested for Total-C, calculated LDL-C, HDL-C, TG, and non-HDL-C, Apo B, Apo A-1, Apo B/Apo A-1 ratio, and Lp(a).
10. For female patients – estradiol, follicle-stimulating hormone (FSH) and luteinizing hormone (LH); for male patients – testosterone, FSH and LH.
11. Dipstick and, if abnormal, microscopy.

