7.3. Handling of Study Drug Discontinuation and Patient Withdrawal from the Study

7.3.1. Study Drug Discontinuation

Study drug should be continued whenever possible. In the event study drug dosing is stopped, it should be determined if the stop can be made temporarily. Permanent discontinuation should be a last resort. In any case, the patient should remain in the study as long as possible.

Patients who prematurely discontinue study drug should remain in the study and undergo all study visits and procedures, with the exception of dosing with study drug. At the time of study drug discontinuation, the patient should have, as soon as possible, an unscheduled visit with the assessments that are normally done at the end of study (EOS) visit (this should take place within 5 days of discontinuation of study drug, if possible), and then resume the original study schedule until end of study.

Assessment of patients who do not consent to remain in the study after discontinuation of study drug should be managed according to Section [7.4.1](#).

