3.1.2. Primary Safety Analysis Set

The primary safety population (PSAF) used to analyze the neurocognitive endpoints will be defined as patients from the safety population who had an assessment of the SWM strategy score at baseline, and at least 1 score measured during the TEAE period. The TEAE period is defined as the first double-blind treatment dose to last dose of double-blind treatment + 70 days (10 weeks). Patients will be analyzed according to the treatment actually received.

In addition:

- Randomized patients for whom it is unclear whether they took the study drug will be included in the safety population as randomized.
- For patients receiving study drug from more than 1 treatment group during the trial, the treatment group allocation for as-treated analysis will be Praluent.

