5.6. Analyses of Primary and Secondary Endpoints

5.6.1. Analyses of Primary Neurocognitive Variable

The primary neurocognitive analysis is a statistical evaluation of the noninferiority of the Praluent 75 mg Q2W/up-titrate 150 mg Q2W dose regimen to placebo for the primary endpoint of change in SWM strategy z-score from baseline to week 96 in the primary safety population. The 2-sided 95% CI for the mean treatment difference at week 96 will be determined using an appropriate contrast statement in a mixed-effect model with repeated measures (MMRM). The upper CI limit will be compared to the noninferiority margin which is defined as 0.2 and the noninferiority will be declared if the upper CI limit is below the noninferiority margin.

In the case noninferiority is achieved for the primary neurocognitive function endpoint comparison, superiority of the primary neurocognitive function endpoint will be assessed using the same upper CI limit calculated for the primary comparison. Specifically, the upper CI limit will be compared to zero and superiority will be declared if the upper CI limit is below zero. A statistical multiplicity adjustment is not needed, since this process of noninferiority achievement followed by superiority assessment using the same 95% upper CI limit on the primary endpoint corresponds to a simple closed test procedure (EMA/CPMP/EWP/482/99 – 27July 2000).

The MMRM model will include the fixed categorical effects of treatment group (placebo, Praluent), both randomization strata (as per IVRS/IWRS), time point (weeks 24, 48, 72, and 96), treatment-by-time point interaction, and strata-by-time point interaction, as well as the continuous covariate of baseline SWM strategy raw score value and baseline value-by-time point interaction. Post-baseline assessments within a patient's TEAE period will be included in the analysis and missing data are accounted for by the MMRM model. Model assumptions for normality will be explored prior to the analysis testing.

This model will be run using Statistical Analysis Software (SAS) mixed procedure with an unstructured correlation matrix to model the within-patient errors. Parameters will be estimated using restricted maximum likelihood method with the Newton-Raphson algorithm. Denominator degrees of freedom will be estimated using Satterthwaite's approximation.

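### A cognitive battery taken at drug discontinuation before day 85 has no analysis window, so an early stopper can count in the primary population yet add no score to the primary model

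*SAP*

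**What the plan says.** - **Collection.** Footnote 8 of the Schedule of Events (protocol 7.1) states that "in case of early treatment discontinuation, an unscheduled neurocognitive battery test will be performed". The same footnote applies to a neurocognitive adverse event reported at a visit without a planned test. Protocol 7.3.1 sets the timing of the stop visit: "this should take place within 5 days of discontinuation of study drug, if possible". The patient then returns to the visit schedule.
- **Population.** SAP 3.1.2 narrows the safety population to those who "had an assessment of the SWM strategy score at baseline, and at least 1 score measured during the TEAE period". That period runs from first dose to last dose plus 70 days. No analysis window is mentioned. The mITT definition in SAP 3.2.2, by contrast, asks for a value both in its on-treatment period and in an analysis window.
- **Model.** SAP 5.6.1 has four time points (weeks 24, 48, 72 and 96), with baseline as a covariate. Post-baseline assessments within a patient's "TEAE period will be included in the analysis and missing data are accounted for by the MMRM model".
- **Windows.** CANTAB falls under "Table 2: Analysis Windows Definition – All Endpoints Except Lipids or Vital Signs" in SAP 10.2. Its Week 24 row covers days 85 to 252, and no row covers days 2 to 84. SAP 6.5 adds: "These analysis windows will be applicable for all analyses, and they are defined to provide more homogeneous data for time point-specific analyses".

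**The concern.** The protocol goes out of its way to obtain a cognitive score at the moment a patient stops drug. For a patient who stops in roughly the first 11 weeks, that score has nowhere to go. SAP 5.6.1 says it is included; Table 2 gives it no time point.

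Three things follow. The primary safety population can be larger than the set of patients the MMRM actually uses. The MMRM and the imputation analyses rest on different patients. And the direction is not neutral: in a noninferiority study of cognition, any early worsening on Praluent that led to stopping would be left out of the primary estimate, and that omission favours noninferiority.

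**Working it through.** **Plan's own figure (background).** With margin 0.2, SD 1.0, true difference 0, one-sided 0.025 and 95% power, the normal approximation gives 650 per group and the noncentral t gives 651 (power 0.9501). Dropout: 651 / (0.80 × 0.75) = 1085. Both stated figures reproduce. The point does not depend on them.

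**Day arithmetic.** Inputs: stop battery by last dose + 5 (protocol 7.3.1); first window day 85 (SAP Table 2); TEAE end = last dose + 70 (SAP 3.1.2); week 24 visit on day 169 ± 3, that is days 166 to 172 (protocol Table 1).

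| Last dose (day) | Battery by day | Table 2 window | TEAE ends (day) | Week 24 visit inside TEAE? |
|---|---|---|---|---|
| 1 | 6 | none | 71 | no |
| 15 | 20 | none | 85 | no |
| 29 | 34 | none | 99 | no |
| 43 | 48 | none | 113 | no |
| 57 | 62 | none | 127 | no |
| 71 | 76 | none | 141 | no |
| 79 | 84 | none | 149 | no |
| 80 | 85 | Week 24 | 150 | no |
| 96 | 101 | Week 24 | 166 | only if held on day 166 |
| 99 | 104 | Week 24 | 169 | yes, if held by day 169 |
| 102 | 107 | Week 24 | 172 | yes |

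A stop battery before day 85 implies a last dose by day 84, so the TEAE period ends by day 84 + 70 = 154, before the earliest week 24 visit (day 166). Unless another battery falls between day 85 and last dose + 70, the patient has no response at any MMRM time point.

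**Where the cut-off lies.** Counting 5 days from the last dose, the gap covers last doses up to day 84 − 5 = 79. If stopping is recognised at the next due dose, it covers last doses up to day 84 − 14 − 5 = 65; a last dose on day 71 then gives a battery on days 85 to 90, inside the window.

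**Number affected (assumption-based).** Treat the planned 20% first-year dropout as drug stopping at constant hazard, with every stopper tested before day 85.

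- By day 65: 1 − 0.8^(65/365) = 3.9%, or 42 of 1085.
- By day 79: 1 − 0.8^(79/365) = 4.7%, or 51 of 1085.
- At 10% per year, 11 weeks: 1 − 0.9^(11/52) = 2.2%, or 24 of 1085.
- Early hazard doubled, 11 weeks: 1 − 0.8^(22/52) = 9.0%, or 98 of 1085.

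**Effect on the week 96 difference (illustrative).** Suppose 4.7% of the Praluent arm only had worsened, and the score carries to week 96 with a slope of 0.6. Neither the worsening nor the slope comes from the documents.

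- 0.5 SD worse: 0.047 × 0.5 × 0.6 = 0.014.
- 1 SD worse: 0.047 × 1.0 × 0.6 = 0.028.

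With 9.0% affected, the same products are 0.027 and 0.054.

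**Imputation analyses.** The multiple-imputation model (SAP 10.5) uses baseline and planned time points, so a day 2 to 84 score has no variable to enter. In the pattern-mixture analysis (SAP 10.6), a value missing after the TEAE period is drawn around the placebo mean at that time point, without reference to the patient's own post-baseline scores.

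**The case against.** The strongest reply is that the SAP expects such patients and that little is lost.

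- **Anticipated pattern.** SAP 5.6.1.2 lists primary-population patients whose score is missing from week 24 onward and describes them by pattern. This stands: a population larger than the modelled set is foreseen. But the SAP does not say that some of these patients have an observed score. The same section plans SWM graphs at weeks 8 and 12, which have no Table 2 window and no scheduled battery.
- **Fewer patients.** The 20% is a dropout rate, whereas drug stoppers are meant to stay in the study. The gap also needs a completed battery before day 85; without any TEAE-period score the patient is not in the population at all. Drug accountability is checked only at re-supply visits (protocol 5.6.3), the first after baseline being week 12. A battery prompted there on day 85 or later is in the window, and in the TEAE period if the last dose was on day 15 or later (15 + 70 = 85). This stands, although the week 8 visit may reveal earlier stops.
- **Wide window.** Table 2 uses equal 168-day bands for homogeneity. A window of days 2 to 252 could label a day 6 retest as week 24. This is a fair reason not to change the primary windows.
- **Unscheduled scores.** SAP 6.6 does not name cognitive tests among the measures that may fill a time point, but SAP 6.7 calls the primary variable an efficacy variable, and efficacy is on the list. Eligibility is probably intended; it should be stated.

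A reader might infer that the imputation analyses overwrite the early score with random draws. They do not: the draws fill missing values at planned time points, including week 96, and the early score is simply unused. A reader might also infer that early cognitive harm disappears from the trial. It does not: neurocognitive events are adjudicated blind and tabulated in the safety population, with no window applied (SAP 4.7.1.2 and 5.7.1).

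**Conclusion.** The gap is real and follows from the documents' own dates. A patient whose only post-baseline TEAE-period score falls on days 2 to 84 belongs to the primary safety population, contributes nothing to the primary MMRM, and is carried in the imputation analyses without that score.

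Its size is uncertain. The 42 to 51 per arm is an upper figure for a 20% first-year stopping rate at constant hazard, since it assumes that every stopper is tested before day 85; other rates move it to about 24 to 98. Under the illustrative assumptions at 4.7% affected, the week 96 difference would shift by roughly 0.01 to 0.03 against a margin of 0.2. Planned power is unaffected, because these patients are already inside the dropout allowance.

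A reader might go further and infer that early stoppers are mainly patients with cognitive harm, or that the noninferiority conclusion is in doubt. The documents support neither. They say nothing about why patients stop early, and protocol 1.1 reports a low incidence of neurocognitive events without imbalance. What holds is the direction: if early worsening on Praluent did lead to stopping, leaving it out would favour noninferiority. That justifies a prespecified check, not a change to the primary analysis.

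**What to change.** Keep the primary windows and add the following to the SAP.

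1. **Sensitivity MMRM.** Rerun the primary model with the CANTAB Week 24 window set to days 2 to 252 and unscheduled batteries explicitly eligible. Apply the TEAE restriction before the nearest-to-day-169 rule. Otherwise a week 24 score taken after the TEAE period would be selected as nearest and then excluded, displacing the early score.
2. **Population.** Define the primary safety population as a baseline score plus at least 1 score that is both in the TEAE period and within an analysis window, in the manner of the mITT. In the sensitivity run, apply this definition with the widened window so that the affected patients are included.
3. **Reporting.** Give, by arm, the number of patients whose only post-baseline TEAE-period score falls on days 2 to 84.

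The cost is SAP wording and one extra run; no new data are needed. There are three limits. Some early stop-visit scores will be labelled week 24 and reach week 96 only through the covariance. The pattern-mixture week 96 draws for these patients would not change. And under the aligned definition, these patients leave the imputation analyses that keep the primary windows, which is why the count in item 3 should be reported.
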